## 7.4 PRIMARY ENDPOINT(S)

To investigate the relative bioavailability of the two formulations (tablet/oral solution) and to investigate the effect of food on the primary PK parameters as defined in [Section 5.1](#), the following comparisons will be made:

- (1) T1 (tablet, fasted) vs. R1 (oral solution, fasted), to investigate the relative bioavailability of the tablet and solution formulations
- (2) T2 (tablet fed) vs. R2 (tablet fasted) , to investigate the effect of food on the tablet formulation

These comparisons will be performed separately on the PKS. For further details about treatments see [Table 6.1: 1.](#)

The primary PK endpoints (see CTP Section 5.5.1 and TSAP [Section 5.1](#)) will be log transformed (natural logarithm) prior to fitting the ANOVA model. For each endpoint, the difference between the expected means for  $\log(T \text{ (fasted)}) - \log(R)$  and  $\log(T \text{ (fed)}) - \log(T \text{ (fasted)})$  will be estimated by the difference in the corresponding adjusted means (Least Squares Means), and a two-sided 90% confidence interval based on the t-distribution will be computed. These quantities will then be back-transformed to the original scale to provide the point estimate and 90% confidence intervals (CIs) for each endpoint. Since the main focus is on estimation (and not testing), an acceptance range was not specified, i.e. no hypothesis will be tested.

**CTP (Section 7.1.3 Model):** *The statistical model used for the analysis of primary endpoints will be an analysis of variance (ANOVA) model on the logarithmic scale. This model will include effects accounting for the following sources of variation: 'sequence', 'subjects nested within sequences', 'period' and 'treatment'. The effect 'subjects within sequences' will be considered as random, whereas the other effects will be considered as fixed. The model is described by the following equation:*

$$Y_{ijkm} = \mu + \zeta_i + s_{im} + \pi_j + \tau_k + e_{ijkm}, \text{ where}$$

$Y_{ijkm}$  = logarithm of response (endpoint, see [CTP] Section 5.5.1) measured on subject  $m$  in sequence  $i$  receiving treatment  $k$  in period  $j$

$\mu$  = the overall mean

$\zeta_i$  = the  $i^{th}$  sequence effect,  $i = 1, 2, 3$

$s_{im}$  = the effect associated with the  $m^{th}$  subject in the  $i^{th}$  sequence,  
 $m = 1, 2, \dots, n_i$

$\pi_j$  = the  $j^{th}$  period effect,  $j = 1, 2, 3$

$\tau_k$  = the  $k^{th}$  treatment effect,  $k = 1, 2, 3$

$e_{ijkm}$  = the random error associated with the  $m^{th}$  subject in sequence  $i$  who received treatment  $k$  in period  $j$

The analysis will be accomplished using the XPKISTAT macro, based on PKS, and the option BWC (Bioavailability/Bioequivalence, within subject design, time-controlled).

[figure not shown]

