mode of admin.:	Oral with 240 mL of water after an overnight fast of at least 10 h (Treatment A) and in fed state (Treatment C)			
Comparator product:	BI 1467335 oral solution formulation			
dose:	10 mg			
mode of admin.:	Oral with 240 mL of water after an overnight fast of at least 10 h (Treatment B)			
Duration of treatment:	One day for each treatment (3 single doses), separated by washout periods of at least 21 days			
Criteria for pharmacokinetics:	Primary endpoints: AUC _{0-tz} and C _{max} of BI 1467335 [REDACTED]			

Proprietary confidential information © 2016 Boehringer Ingelheim International GmbH or one or more of its affiliated companies

Name of company: Boehringer Ingelheim		Tabulated Trial Protocol		
Name of finished product: Not applicable				
Name of active ingredient: BI 1467335				
Protocol date: 12 October 2016	Trial number: 1386.17		Revision date: Not applicable	
Criteria for safety: Adverse events (AEs) including clinically relevant findings from the physical examination, safety laboratory tests, 12-lead electrocardiogram (ECG), vital signs (blood pressure [BP], pulse rate [PR])				
Statistical methods: Relative bioavailability will be estimated by the ratios (tablet formulation fasted/oral solution fasted; tablet fed/tablet fasted) of the geometric means for the primary endpoints. Additionally, their two-sided 90% confidence intervals (CIs) will be provided. This method corresponds to the two one-sided t-tests procedure, each at the 5% significance level. Since the main focus is on estimation and not testing, an acceptance range is not specified. The statistical model will be an ANOVA on the logarithmic scale including effects for 'sequence', 'subjects nested within sequences', 'period' and 'treatment'. CIs will be calculated based on the residual error from ANOVA. Descriptive statistics will be calculated for all endpoints.				

FLOW CHART

Period	Visit	Day	Planned time (relative to first drug administration) [h:min]	Approximate clock time of actual day [h:min]	Event and comment	Safety laboratory	PK _{blood}	12-lead ECG	Vital signs (BP, PR)	Questioning for AEs and concomitant therapy ⁶
SCR	1	-21 to -1			Screening (SCR) ¹	x		x	x	
1/2/3 (three identical periods with a wash-out of at least 21 days)	2/3/4	-5 to -1	-123:00		Visits 3 and 4 only	x ⁸				x ⁸
		-1	-12:00	20:00	Admission to trial site ⁷	x ^{5,7}				x ⁷
		1	-1:00	07:00	Allocation to treatment ² (Visit 2 only)	x ²	■	x ²	x ²	x ²

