3. DESCRIPTION OF DESIGN AND TRIAL POPULATION

3.1 OVERALL TRIAL DESIGN AND PLAN

The study will be performed as a randomised, open-label, single dose, three-way crossover trial in healthy male subjects in order to compare the tablet under fasted conditions (Treatment A) to the oral solution under fasted conditions (Treatment B) and to assess the food effect on the PK of BI 1467335 by comparing the tablet under fed conditions (Treatment C) with the tablet under fasted conditions (Treatment A).

A total of 18 healthy male subjects are planned to participate in the trial. Subjects will be randomly allocated to 3 treatment sequences (ABC, BCA and CAB). The treatments will be 2 x 5 mg BI 1467335 tablet in the fasted state (Treatment A), 10 mg BI 1467335 oral solution in the fasted state (Treatment B) and 2 x 5 mg BI 1467335 tablet in fed state after a high caloric breakfast (Treatment C). For details, see [Section 4.1](#).

There will be a washout period of at least 21 days between drug administrations in consecutive treatment periods.

[figure not shown]
An overview of all relevant trial activities is provided in the [Flow Chart](#). For visit schedule and details of trial procedures at selected visits, refer to [Sections 6.1](#) and [6.2](#), respectively.

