4.1.5 Blinding and procedures for unblinding

No blinding will be performed because treatments are distinguishable from each other.

This Phase I trial will be handled in an open fashion throughout (i.e. during the conduct, including data cleaning and preparation of the analysis). This is considered acceptable because the potential for bias seems to be low and does not outweigh practical considerations.

Emergency envelopes will not be provided, since all subjects receive the same dose of different formulations in an open label design.

PK samples will be labelled in such a way that treatment allocation cannot be derived by the analytical site.

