7.6 DETERMINATION OF SAMPLE SIZE

It is planned to include a total of 18 subjects in the trial because this sample size is considered sufficient to achieve the aims of this exploratory trial.

With this sample size, the below precision of the ratio of geometric means (test/reference) can be expected. Precision is defined as the ratio of upper to lower confidence interval limit.

Note that the precision is independent of the actual ratio of geometric means.

The observed geometric coefficient of variation (gCV) for BI 1467335 after single oral doses of 10 mg [REDACTED] BI 1467335 was 104% for AUC_{0-tz} and 94% for C_{max} [REDACTED] [REDACTED], [a href="c09036683">c09036683]. The reported variability listed in this trial (calculated from 6 individuals) originates from a parallel group design and is an estimate of the total variability and not of the between-subject variability. For a crossover study, an estimate of the intra-individual gCV is needed. Together with the correlation between two responses of the same subject ρ , we can estimate the intra-individual variability out of the total variability. A reasonable range for ρ in PK trials based on former experience is 0.6 to 0.7, where $\rho = 0.6$ is the conservative choice. [Table 7.6: 1](#) provides an overview of the resulting intra-individual gCVs.

Table 7.6: 1 Estimates of the intra-individual gCV

ρ	Endpoint	gCVT*	σ_T^2	σ_W^2	gCVw**
0.6	C_{\max}	94%	0.635	0.254	53.8%
	AUC_{0-tz}	104%	0.733	0.293	58.4%
0.7	C_{\max}	94%	0.635	0.190	45.8%
	AUC_{0-tz}	104%	0.733	0.220	49.6%

* gCV indicates the gCV for total variability.

** gCVw indicates the gCV for intra-individual variability

Assuming a gCV of 58.4% for AUC_{0-tz} of BI 1467335 and given the chosen sample size of 18 subjects, the precision of the two-sided 90% confidence interval of the gMean ratio will be approximately 2.09 (upper confidence limit/lower confidence limit); for a larger correlation of $\rho = 0.7$ and assumed intra-individual gCV of 49.6% for AUC_{0-tz} of BI 1467335, the precision would be approximately 1.89.

[Table 7.6: 2](#) provides an overview of the 90% confidence intervals that are expected with 95% probability, for possible scenarios of the ρ , gCV and intra-subject ratios (T/R).

Table 7.6: 2

Precision and expected two-sided 90% confidence intervals around the ratios of geometric means for different correlations (ρ) and ratios in a 3x3x3 cross-over trial (N=18)

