#### **4. CHANGES IN THE PLANNED ANALYSIS OF THE STUDY**

All analyses described in this TSAP are in accordance with the statistical methods described in the CTP version 1.0.

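### Does the SAP's instruction to perform the two primary comparisons separately undo the precision planned in the protocol?

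*SAP*

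**What the plan says.** SAP section 7.4 labels fasted tablet against oral solution T1 and R1, and fed tablet against fasted tablet T2 and R2. It then says: "These comparisons will be performed separately on the PKS". The next paragraph log-transforms each endpoint before fitting one ANOVA model and estimates both log differences from the adjusted means. The section repeats the model of Protocol section 7.1.3, with three sequences, three periods and a treatment index running from 1 to 3.

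The protocol synopsis fixes the error term: "CIs will be calculated based on the residual error from ANOVA". Protocol section 7.6 derives the expected precision, defined as upper over lower confidence limit, for the three-treatment design. For AUC0-tz with an intra-individual gCV of 58.4%, "the precision of the two-sided 90% confidence interval of the gMean ratio will be approximately 2.09". SAP section 4 states: "All analyses described in this TSAP are in accordance with the statistical methods described in the CTP version 1.0".

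**The concern.** The sentence in SAP section 7.4 is the SAP's own addition; the protocol has no counterpart. The fasted tablet carries two labels, T1 in one pair and R2 in the other, which encourages a programmer to run one call per pair and leave out the third treatment. The readable text never states the residual degrees of freedom, nor says outright that the third treatment's data enter each comparison.

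The choice sets the residual variance and degrees of freedom behind every primary 90% interval, and in an estimation trial those intervals are the main inferential result. Under Protocol section 4.1.5 the trial "will be handled in an open fashion throughout (i.e. during the conduct, including data cleaning and preparation of the analysis"). If the model really were open, it could in principle be settled after results were known. The sample-size section would then describe an analysis that was not the one performed.

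**Working it through.** **Inputs.** Protocol section 7.6 gives 18 subjects and the design, "in a 3x3x3 cross-over trial (N=18"). Protocol section 3.1 gives the sequences ABC, BCA and CAB; with 1:1:1 allocation (section 7.5) that is 6 subjects each. The intra-individual gCVs in Table 7.6: 2 are 58.4% and 49.6% for AUC0-tz, and 53.8% and 45.8% for Cmax. The intervals are two-sided 90%, and the tabulated limits are those expected with 95% probability.

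**Residual degrees of freedom**, from the rank of the design matrix with complete data:

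- One three-treatment fit: 18 × 3 = 54 observations. Parameters: 18 subjects + 2 periods + 2 treatments = 22. Residual: 54 − 22 = 32.
- One two-treatment fit (A with B, or A with C): 18 × 2 = 36 observations. Parameters: 18 + 2 + 1 = 21. Residual: 36 − 21 = 15.

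The variance of a treatment contrast is 2σ²/18 in both cases.

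**Formula.** Precision = exp(2 × t(0.95, df) × SE × f), where SE = √(2σ²/18), σ² = ln(1 + gCV²) and f = √(χ²(0.95, df)/df). The factor f is the 95% probability allowance.

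**AUC0-tz at ρ = 0.6.** σ² = ln(1 + 0.584²) = 0.2935, so SE = √(2 × 0.2935/18) = 0.1806.

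- 32 df: t = 1.694, f = √(46.19/32) = 1.201. Precision = exp(2 × 1.694 × 0.1806 × 1.201) = 2.085, the protocol's 2.09 to rounding.
- 15 df: t = 1.753, f = √(25.00/15) = 1.291. Precision = exp(2 × 1.753 × 0.1806 × 1.291) = 2.264.

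| Endpoint, ρ | Protocol | One fit, 32 df | Two fits, 15 df each |
|---|---|---|---|
| AUC0-tz, 0.6 | 2.09 | 2.085 | 2.26 |
| Cmax, 0.6 | 1.98 | 1.98 | 2.14 |
| AUC0-tz, 0.7 | 1.89 | 1.89 | 2.03 |
| Cmax, 0.7 | 1.81 | 1.81 | 1.93 |

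All four protocol figures match the joint model and none matches the separate fits. Protocol section 7.6 was therefore computed for one pooled three-treatment ANOVA.

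**Size of the difference if two fits were run** (AUC0-tz, ρ = 0.6):

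- Interval around a ratio of 100%, at the 95% limit: 69–144% with one fit, about 66–150% with two.
- Probability of a precision of 2.09 or better: about 95% against 84%.
- Without the factor f: exp(2 × 1.694 × 0.1806) = 1.84 against exp(2 × 1.753 × 0.1806) = 1.88.
- Point estimates: identical with complete data.

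**Which reading the text supports.** A two-treatment fit has two treatment levels, but the model in SAP section 7.4 has three. That section speaks of the model in the singular and derives both differences from its least squares means. The synopsis takes the intervals from the residual error of that ANOVA, and SAP section 4 declares no change. The word at issue qualifies the comparisons, not the models or the datasets. Two contrasts reported separately from one fit satisfy it; two fits would contradict the model equation in the same section.

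**The case for a change.** The strongest reply is that a better reading is not a specification. The model equation is copied from the protocol, whereas the sentence about separate comparisons is the SAP's own, and a SAP exists to remove such doubt. The macro option named at the end of SAP section 7.4 does not visibly settle which data enter each comparison.

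Nor need the two approaches agree closely in a single trial. In 40,000 simulated trials with both fits on the same data, the ratio of log widths (separate over joint) had a median of 1.03 and a 5th to 95th percentile range of 0.79 to 1.24; the widths differed by more than 10% in about half of the trials.

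The arithmetic stands, and so does the remark that the sentence is loosely worded. The rest carries less weight. The width differences run in both directions: the separate-fit interval was more than 10% narrower in about 18% of trials. They reflect noise in two estimates of the same variance, not bias. Open handling of treatment allocation does not leave open a model that both documents write out. Part of the specification is also not visible: a figure after the macro statement is missing, and the macro's behaviour is defined elsewhere. The readable text therefore cannot show that the fitting call was left unspecified.

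Nor does either approach dominate. Suppose, as an assumption with no basis in the documents, that the within-subject variance in the fed arm were twice or half that of the others. The joint fit's 90% interval would then cover about 94% or 87% for tablet against solution, and 88% or 92% for the food effect, while separate fits would stay at about 90%. Pooling gains degrees of freedom in exchange for relying on equal variances. That is a fair trade-off, and the protocol made it.

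**Conclusion.** No change is needed. Read as a whole, the plan specifies one three-treatment ANOVA per endpoint with two contrasts taken from it. That model has 32 residual degrees of freedom and reproduces all four precisions in Protocol section 7.6. No two statements conflict and no stated figure is wrong. An analyst following the equation in SAP section 7.4 would fit this model.

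A literal reading of the one loose sentence would cost little. The 95%-probability precision for AUC0-tz would go from 2.09 to about 2.26, the ratio without that allowance from 1.84 to 1.88, and the intervals would still be valid 90% intervals. The trial is exploratory, tests no hypothesis and sets no acceptance range, so no conclusion turns on a difference of that size.

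These figures assume 18 subjects with complete data, the protocol's gCVs and, apart from the stated variance scenarios, equal within-subject variance across the three treatments.

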## **7.5        SECONDARY ENDPOINT(S)**

### **7.5.1      Key secondary endpoint(s)**

This section is not applicable as no key secondary endpoint has been specified in the protocol.

### **7.5.2      (Other) Secondary endpoint(s)**

This section is not applicable as no secondary endpoint has been specified in the protocol.

## **7.7 EXTENT OF EXPOSURE**

Descriptive statistics are planned for this section of the report based on the TS. The date and time of drug administration will be listed for each subject.

## **7.8 SAFETY ANALYSIS**

All safety analyses will be performed on the TS. The analyses will be done by ‘treatment at onset’(concept of ‘treatment emergent AEs’).

**CTP (Section 7.3.3 Safety analyses):** *Treatments will be compared in a descriptive way. Tabulations of frequencies/proportions will be used for the evaluation of categorical (qualitative) data, and tabulations of descriptive statistics will be used to analyse continuous (quantitative) data.*

### **7.8.1 Adverse events**

AEs will be coded with the most recent version of MedDRA.

Unless otherwise specified, the analyses of adverse events will be descriptive in nature. All analyses of AEs will be based on the number of subjects with AEs and NOT on the number of AEs.

Furthermore, for analysis multiple AE occurrence data on the CRF will be collapsed into an AE event provided that all of the following applies:

- All AE attributes are identical (lowest level term (LLT), intensity, action taken, therapy required, seriousness, reason for seriousness, relationship, outcome, AE of special interest)

- The occurrences were time-overlapping or time-adjacent (time-adjacency of 2 occurrences is given if the second occurrence started in the same hour in which the first occurrence ended)

For further details on summarization of AE data, please refer to the guideline 'Handling and summarization of adverse event data for clinical trial reports and integrated summaries' ([4](#)) [001-MCG-156].

**CTP (Section 5.2.2.1 Definitions of adverse events):** *The following are considered as AESIs in this trial:*

*Hepatic injury, as defined by the following alterations of hepatic laboratory parameters:*

- *An elevation of AST and/or ALT  $\geq 3$ -fold ULN combined with an elevation of total bilirubin  $\geq 2$ -fold ULN measured in the same blood sample, and/or*
- *Marked peak aminotransferase (ALT, and/or AST) elevations  $\geq 10$  fold ULN*

*These lab findings constitute a hepatic injury alert and the patients showing these lab abnormalities need to be followed up according to the 'DILI checklist' provided in the ISF. In case of clinical symptoms of hepatic injury (icterus, unexplained encephalopathy, unexplained coagulopathy, right upper quadrant abdominal pain, etc.) without lab results (ALT, AST, total bilirubin) available, the Investigator should make sure that these parameters are analysed, if necessary in an unscheduled blood test. Should the results meet the criteria of hepatic injury alert, the procedures described in the DILI checklist should be followed.*

According to ICH E3 ([5](#)) AEs classified as 'other significant' needs to be reported and will include those non-serious and non-significant adverse events with  
(i) 'action taken = discontinuation' or 'action taken = reduced', or  
(ii) marked haematological and other lab abnormalities or lead to significant concomitant therapy as identified by the Clinical Monitor/Investigator at a Medical Quality Review Meeting.

The analysis of AEs will be based on the concept of treatment emergent AEs. That means that all adverse events occurring between first drug intake till last drug intake + residual effect period will be assigned to the randomised treatment. All adverse events occurring before first drug intake will be assigned to 'screening' and all adverse events occurring after the residual effect period will be assigned to "follow-up" (for listings only). For details on the treatments and the definition of study phases, see [Section 6.1](#).

An overall summary of AEs will be presented.

The frequency of subjects with AEs will be summarised by treatment, primary system organ class and preferred term. Separate tables will be provided for subjects with serious AEs, subjects with AESIs, and subjects with other significant AEs (according to ICH E3 ([5](#))). AEs which were considered by the investigator to be drug related will be summarised separately. AEs will also be summarised by maximum intensity. The system organ classes will be sorted

according to the standard sort order specified by the European Medicines Agency (EMA), preferred terms will be sorted by frequency (within system organ class).

Separate listings will be provided for all AEs, for serious AEs, for AESIs, for other significant AEs (according to ICH E3), for serious AEs, AESIs or other significant AEs, and for non-serious AEs that had an incidence of > 5% for at least one treatment.

The analysis of AEs will be based on the concept of treatment emergent AEs. For details on the treatments and the definition of study phases, see [Section 6.1](#).

An overall summary of AEs will be presented.

#### **7.8.2      Laboratory data**

**CTP (Section 7.3.3 Safety analyses):** *Laboratory data will be compared to their reference ranges. Values outside the reference range as well as values defined as clinically relevant will be highlighted in the listings. Additionally, differences from baseline will be evaluated.*

The analyses of laboratory data will be based on BI standards (6). Descriptive statistics of laboratory values over time and for the difference from baseline will be provided. Frequency tables of changes between baseline and last value on treatment with respect to the reference range will be presented.

Possibly clinically significant abnormal laboratory values are only those identified either in the Investigator's comments on the database or at the RPM/DBLM at the latest. It is the investigator's responsibility to decide whether a lab value is clinically significant abnormal or not. Standard or project-specific rules for flagging clinically significant values will not be applied in this study. Possibly clinically significant abnormal laboratory values will only be presented within the scope of the listing of investigator comments.

